X You will store identifiers separately from the study data, with no link between the identifiers and the study data. Describe the data to which this applies:

New activities for all MSM/TGP" and "New activities for PrEP providers, (prescribers, caseworkers and peer educators/navigators, etc):

Interested participants will be given a date for their interview. No participant identifiable information will be documents or recorded. Once an interview is completed, the audio recordings will be uploaded to a secure transcription service and labeled only by the interview date to avoid any direct or indirect identifiable information. This process of labeling will be the same for transcripts. Once transcriptions are returned and reviewed for accuracy, the audio file will be permanently deleted.

The demographic survey information will be entered in by a study staff coordinator and will not be tied to any participant identifiable information. It will only be tied to the interview date to avoid any direct or indirect.

d. Research collaboration. Will individuals who provide you with coded information or specimens for your research also collaborate on other activities for this research? If yes, identify the activities and provide the name of the collaborator's institution/organization.

Examples include but are not limited to: (1) study, interpretation, or analysis of the data that results from the coded information or specimens; and (2) authorship on presentations or manuscripts related to this work.

No, individuals who provide us with coded information or specimens will not collaborate on other activities for this research.

5.6 Newborn dried blood spots. Will you use newborn dried bloodspots collected in the United States on or after March 18, 2015?

No

Yes

→ If yes, is this research supported by any federal funding (including any fellowship or career development award that provides salary support)?

No

Yes

→ If yes, describe how you will ensure that the bloodspots were collected with parental permission (in compliance with a 2015 law that applies to federal-funded research).

5.7 Protected Health Information (PHI). Will you access, obtain, use, or disclose a participant's identifiable PHI for any reason (for example, to identify or screen potential subjects, to obtain study data or specimens, for study follow-up) that does not involve the creation or obtaining of a Limited Data Set?

PHI is individually-identifiable healthcare record information or clinical specimens from an organization considered a "covered entity" by federal HIPAA regulations, in any form or media, whether electronic, paper, or oral. If you will use UW Medical Records, you must answer yes to this question.

	No
	Yes

No → If no, skip the rest of this question; go to [question 5.8](#)

Yes → If yes, answer all of the questions below.

a. Describe the PHI you will access or obtain, and the reason for obtaining it. *Be specific.*

We will obtain the health information that is in the clinical charts at the study sites where participants are enrolled that is relevant to PrEP follow-up. All participants will sign a HIPAA Authorization and an ROI at study entry. This data will include appointment dates, behavioral eligibility for PrEP, any reported side effects from PrEP, prescription orders and refills, reported PrEP adherence, any discontinuation of PrEP and reason, and other information that may be recorded regarding their PrEP use and follow-up.

b. Is any of the PHI located in Washington State?

	No
	Yes

c. Describe how you will access or obtain the PHI. *Be specific.*

At study entry, all participants will sign a HIPAA Authorization and an ROI between the clinic site and the UW study team to share PrEP-related clinical records.

d. For which PHI will you obtain HIPAA authorization from the subjects by having them sign a HIPAA Authorization form, before obtaining and using the PHI?

We will ask participants to authorize us to access their PrEP-related medical records using both a HIPAA Authorization and an ROI prior to obtaining any PHI.

Confirm by checking the box that you will use the UW Medicine [HIPAA Authorization](#) form maintained on the HSD website if you will access, obtain, use, or disclose UW Medicine PHI.

	Confirmed
-------------------------------------	-----------

e. For which PHI will you NOT obtain HIPAA authorization from the subjects?

None.

Provide the following assurances by checking the boxes.

The PHI will not be reused or disclosed to any other person or entity, except as required by law, for authorized oversight of the research study, or for other research for which the use or disclosure of PHI would be permitted.

You will fulfill the HIPAA "accounting for disclosures" requirement. See [UW Medicine Privacy Policy #25](#). THIS IS ONLY FOR UW RECORDS.

There will be reasonable safeguards to protect against identifying, directly or indirectly, any patient in any report of the research.

5.8 Genomic data sharing. Will you obtain or generate genomic data (as defined at <http://osp.od.nih.gov/scientific-sharing/genomic-data-sharing-faqs/>)?

No

Yes

→ If yes, answer the question below.

a. Do you plan to send genomic data from this research to a national database (for example, NIH's dbGaP database)?

No

Yes

→ If yes, complete the [ZIPLINE SUPPLEMENT Genomic Data Sharing](#) and upload it to the **Supporting Documents** SmartForm of [Zipline](#).

5.9 Whole genome sequencing. For research involving biospecimens: Will the research include whole genome sequencing?

Whole genome sequencing is sequencing of a human germline or somatic specimen with the intent to generate the genome or exome sequence of that specimen.

No

Yes

5.10 Data and specimen sharing/banking. Are you likely to share some or all of the data, specimens, or subject contact information with other researchers or a repository/database for research purposes not related to this study, or to bank them for your own future unspecified research uses? **You are strongly encouraged to consider the broadest possible future plans you might have, and whether you will obtain consent now from the subjects for future sharing or unspecified uses.** Answer **YES** even if you will only share information without identifiers. Answer **NO** if you are unlikely to do any sharing, or if your only sharing will be through the NIH Genomic Data Sharing described in [question 5.8](#).

Many federal grants and contracts now require data or specimen sharing as a condition of funding, and many journals require data sharing as a condition of publication. "Sharing" may include: informal arrangements to share your banked data/specimens with other investigators; establishing a repository from which you formally share with others through written agreements; or sending your data/specimens to a third party repository/archive/entity such as the Social Science Open Access Repository (SSOAR), or the UCLA Ethnomusicology Archive.

No

Yes

→ If yes, answer all of the questions below.

a. Describe what will be stored, including whether any direct or indirect (e.g., subject codes) identifiers will be stored.

b. Describe what will be shared, including whether direct identifiers will be shared and (for specimens) what data will be released with the specimens.

c. Who will oversee and/or manage the sharing?

d. Describe the possible future uses, including limitations or restrictions (if any) on future uses or users. As stated above, consider the broadest possible uses.

Examples: data will be used only for cardiovascular research; data will not be used for research on population origins.

e. Consent. Will you obtain consent now from subjects for the banking and/or future sharing?

No

Yes

→ If yes, be sure to include the information about this consent process in the consent form (if there is one) and in your answers to the consent questions in [Section 8](#).

f. Withdrawal. Will subjects be able to withdraw their data/specimens from banking or sharing?

No

Yes

→ If yes, describe how, and whether there are any limitations on withdrawal.

Example: data can be withdrawn from the repository but cannot be retrieved after they are released.

g. Agreements for sharing or release. Confirm by checking the box that you will comply with UW (and, if applicable, UW Medicine) policies that require a formal agreement between you and the recipient for release of data or specimens to individuals or entities other than federal databases.

Confirmed

5.11 Communication with subjects during the study. Describe the types of communication (if any) you will have with already-enrolled subjects during the study. Provide a description instead of the actual materials themselves.

Examples: email, texts, phone, or letter reminders about appointments or about returning study materials such as a questionnaire; requests to confirm contact information.

For all participants we will send them a link to the survey at baseline, month 3 and month 6 and reminders if they do not complete it. For the participants assigned to the standard of care group, we will not have additional contact. For participants in the peer navigation group, the peer navigator will have varied communication (in-person, email, phone, text) in response to the requests of the participant. Once participants have completed their 6-month survey, or if they discontinue the study early, we will contact them and ask if they would like to participate in an end-of-study interview.

New activities for all MSM/TGP participants and PrEP providers:

Interested participants for the in-depth interview will be contacted by the study team or PI and asked if they would like to participate in the population-appropriate in-depth interview.

5.12 Future contact with subjects. Do you plan to retain any contact information you obtain for your subjects so that they can be contacted in the future?

	No
	Yes

→ If yes, describe the purpose of the future contact, and whether use of the contact information will be limited to your team; if not, describe who else could be provided with the contact information. Describe your criteria for approving requests for the information.

Examples: inform subjects about other studies; ask subjects for additional information or medical record access that is not currently part of the study proposed in this application; obtain another sample.

5.13 Alternatives to participation. Are there any alternative procedures or treatments that might be advantageous to the subjects?

If there are no alternative procedures or treatments, select "No". Examples of advantageous alternatives: earning extra class credit in some time-equivalent way other than research participation; obtaining supportive care or a standard clinical treatment from a health care provider instead of participating in research with an experimental drug.

	No
	Yes

→ If yes, describe the alternatives.

5.14 Upload to the Supporting Documents SmartForm of **Zipline** all data collection forms (if any) that will be directly used by or with the subjects, and any scripts/talking points you will use to collect the data. Do not include data collection forms that will be used to abstract data from other sources (such as medical or academic records, or video recordings).

- *Examples: survey, questionnaires, subject logs or diaries, focus group questions.*
- *NOTE: Sometimes the IRB can approve the general content of surveys and other data collection instruments rather than the specific form itself. This prevents the need to submit a modification request for future minor changes that do not add new topics or increase the sensitivity of the questions. To request this general approval, use the text box below to identify the questionnaires/surveys/ etc. for which you are seeking this more general approval. Then briefly describe the scope of the topics you will cover and the most personal and sensitive questions. The HSD staff person who screens this application will let you know whether this is sufficient or whether you will need to provide more information.*
- *For materials that cannot be uploaded: upload screenshots or written descriptions that are sufficient to enable the IRB to understand the types of data that will be collected and the nature of the experience for the participant. You may also provide URLs (website addresses) or written descriptions below. Examples of materials that usually cannot be uploaded: mobile apps; computer-administered test; licensed and restricted standardized tests.*
- *For data that will be gathered in an evolving way: This refers to data collection/questions that are not pre-determined but rather are shaped during interactions with participants in response to observations and responses made during those interactions. If this applies to your research, provide a description of the process by which you will establish the data collection/questions as you interact with subjects, how you will document your data collection/questions, the topics you plan to address, the most sensitive type of information you will plan to gather, and the limitations (if any) on topics you will raise or pursue.*

Use this text box (if desired) to provide:

- Short written descriptions of materials that cannot be uploaded, such as URLs
- A description of the process you will use for data that will be gathered in an evolving way.
- The general content of questionnaires, surveys and similar instruments for which you are seeking general approval. (See the **NOTE** bullet point in the instructions above.)

5.15 Send HSD a Confidentiality Agreement if you will obtain or use any private identifiable UW records without subject's written consent (for example, screening medical records or class grades to identify possible subjects).

The Confidentiality Agreement form must be completed, printed, signed, and mailed to the Human Subjects Division at [name]. Your IRB application cannot be approved until we receive the Confidentiality Agreement.

6 CHILDREN (MINORS) and PARENTAL PERMISSION

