b. Experience and preliminary work. Briefly describe experience or preliminary work or data (if any) that you or your team have that supports the feasibility and/or safety of this study.

It is not necessary to summarize all discussion that has led to the development of the study protocol. The IRB is interested only in short summaries about experiences or preliminary work that suggest the study is feasible and that risks are reasonable relative to the benefits. Examples: You have already conducted a Phase 1 study of an experimental drug which supports the Phase 2 study you are now proposing to do; you have already done a small pilot study showing that the reading skills intervention you plan to use is feasible in an after-school program with classroom aides; you have experience with the type of surgery that is required to implant the study device; you have a study coordinator who is experienced in working with subjects who have significant cognitive impairment.

We have conducted two surveys, five focus groups, and interviews with the target population under study #54. Through this work, barriers that meth users face to both initiate and adhere to PrEP have been discussed. We have received positive feedback from both the peer educators and other community members that text messages and peer navigation would be acceptable interventions to evaluate for PrEP use with this population and would likely help people take their PrEP. Furthermore, we have asked members of the target population for feedback regarding our messages, educational materials, and what activities the peer should provide, and have incorporated those suggestions into the study to help increase acceptability and usefulness to the participants.

As the study enrollment date is ending, we hope to gather further qualitative information from 2 populations of interest to better understand the challenges/barriers to engaging and retaining MSM/TGP who use meth in the PrEP continuum through in-depth interviews.

1.9 Supplements. Check all boxes that apply, to identify Supplements you should complete and upload to the **Supporting Documents** SmartForm in **Zipline**.

This section is here instead of at the end of the form to reduce the risk of duplicating information in this IRB Protocol form that you will need to provide in these Supplements.

Check all That Apply	Type of Research	Supplement Name

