3 NON-UW RESEARCH SETTING

Complete this section only if your research will take place outside of UW and Harborview

3.1 Reason for sites. Describe the reason(s) why you selected the sites where you will conduct the research.

We will still operate the study out of Gay City and Kelley-Ross pharmacy, and the reasons for selecting those sites are below. At this time we propose to broaden study sites to any provider or organization in King County who provides PrEP to someone who is eligible (for example, Madison Clinic at Harborview, Public Health King County STD clinic, private practitioners) and contacts us if the person is interested in participating. During the

first few months of this study we have seen a very small number of eligible people at Gay City and Kelley-Ross (recent methamphetamine use and seeking PrEP). We have brainstormed and asked community partners regarding approaches to broaden our reach to engage with more individuals who may be eligible and interested to enroll in the study. We have provided study information to colleagues and community partners and believe that some may have persons who seek PrEP from them and would be interested in participating in this study. Furthermore, aside from the consent process and fingerstick dried blood spot collection all research procedures (e.g., peer navigation, surveys) are done outside of the study site.

We selected two non-UW sites to participate in this study: Gay City and Kelley-Ross. These sites were selected for several reasons. First, both Gay City and Kelley-Ross have dedicated PrEP clinics, where meth-using MSM/TG (the target population) seek PrEP. Second, the UW research team has existing relationships with both clinic's leadership, and the PI, [name], is the Medical Director and PrEP provider at Gay City. Finally, in the surveys we did as part of study #54, we asked meth-using MSM/TG where they would like to access PrEP and both Gay City and Kelley-Ross were in the top half in both surveys with 33% saying they would like to get PrEP at Gay City and 27% saying Kelley-Ross in our final survey.

3.2 Local context. Culturally-appropriate procedures and an understanding of local context are an important part of protecting subjects. Describe any site-specific cultural issues, customs, beliefs, or values that may affect your research or how it is conducted.

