Example: A school district may require you to obtain permission from the head district office as well as school principals before approaching teachers or students; a factory in China may allow you to interview factory workers but not allow you to pay them.

There are no additional administrative or ethical requirements that would affect our research at any study site.

4 RECRUITING and SCREENING PARTICIPANTS

4.1 Recruiting and Screening. Describe how you will identify, recruit, and screen subjects. Include information about: how, when, where, and in what setting. Identify who (by position or role, not name) will approach and recruit subjects, and who will screen them for eligibility.

Participants will be recruited at sites in King County that offer PrEP, including Gay City and Kelley-Ross. Clinic staff will identify eligible participants who meet the clinic's criteria for PrEP and report meth use in the prior 3 months, are MSM/TG, have a cell phone, are over 18 years old, and understand English. The clinic staff will be able to identify eligible participants based on the clinical intake questions that are asked as part of regular PrEP screening. Clinic staff will inform potential participants that they are eligible to receive PrEP and will discuss PrEP initiation prior to inviting them to participate in the study. Once clinic staff recognize that someone may be eligible for the study they will inform them of the study and ask if they want to hear more about it.

We may also use recruitment materials at the clinics (e.g., in the waiting room) that describe the study, so a potential participant may inquire about the study prior to the clinic staff bringing it up. Written materials describing the study may be especially important, as anecdotally we have heard that meth users who are currently in the PrEP program at Kelley-Ross have disclosed their meth use after they initiated PrEP, at a follow-up appointment. Since people for this study are only eligible at the visit they are starting PrEP, we may include materials in the waiting room that describe the study to support disclosure of meth use at their first PrEP visit if someone reads about it and is interested in participating in the study.

In addition, during routine clinical care visits, calls, or other points of contact, Gay City clinic staff may tell patients about the study and refer them to the study team for more information.

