5 PROCEDURES

5.1 Study procedures. Using lay language, provide a complete description of the study procedures, including the sequence, intervention or manipulation (if any), drug dosing information (if any), use of records, time required, and setting/location. If it is available and you think it would be helpful to the IRB: Upload a study flow sheet or table to the **Supporting Documents** SmartForm in **Zipline**.

For studies comparing standards of care: It is important to accurately identify the research procedures. See UW IRB [POLICY: Risks of Harm from Standard Care](#) and the draft guidance from the federal Office of Human Research Protections, ["Guidance on Disclosing Reasonably Foreseeable Risks in Research Evaluating Standards of Care"](#); October 20, 2014.

This research study will be conducted in addition to standard of care procedures for PrEP use. Therefore, clinical procedures, including blood draws for laboratory testing, STI screening, PrEP prescriptions, and adherence counseling will be performed in accordance with the clinic's standard of care. Participants will be followed in this study and have visits at entry (baseline), and then at months 1, 3 and 6.

The research procedures, in addition to informed consent, that all participants will get in addition to the standard of care, are the following:

- Randomization: After consent has been obtained the clinical site will send documentation of eligibility (checklist) and the signed informed consent, HIPAA authorization, and ROI to the study team at UW. The site will either email the documents or provide them in person to a study team member. Once these documents are received, the research coordinator will send the participant a link to the baseline survey. After completion of the baseline survey, the participant will be randomized to one of the two intervention groups: standard of care, or peer navigation. The research coordinator will open a sequentially numbered, sealed envelope with the study allocation (generated by site using blocked randomization with variable block sizes and random number generator). They will record the treatment assignment of the participant in their de-identified chart and send a text or email to inform the participant of their assignment.

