In order to obtain consent, the clinical/study staff will meet with an interested and eligible participant in a private setting and review the UW HSD-approved consent form with them. If the staff has a time conflict or are at a site outside of Gay City or Kelley-Ross the clinic staff will reach out to the UW study team (Principal Investigator, Study Coordinator and/or Peer Navigator) to provide consent. In these cases one of the UW study team members will consent the individual within 7 days at either at the study site or in another private location at UW or with a community partner (e.g., a private room at Gay City). All personnel who perform consent will ensure that the participant knows that participating in research is voluntary and that they can stop their participation at any time. Specifically, the clinical/study staff will inform the individual that they can receive PrEP at the clinic without participating in the study, if they would prefer not to participate. Once the consent is reviewed, all questions have been answered, and the staff is confident the client understands the procedures, the client and the staff will both sign and date the consent form.

The Gay City PrEP clinic also offers PrEP visits by telemedicine for people who cannot come to the Wellness Center during the weekly clinic hours and at outreach settings where Gay City offers HIV testing, including UTOPIA in Kent, WA. Telemedicine visits are only done for the initial PrEP visit for clients; for follow-up PrEP visits the HIV tester will see the client without the provider's presence via telemedicine. During the initial visit the HIV tester is with the client in-person and uses a HIPAA-compliant telemedicine platform (Zoom) through their UW Net ID account to connect with the provider. Together, the tester and provider conduct the visit, including informing the client about PrEP, assessing for eligibility, and determining next steps (e.g., how to help client with insurance/financial assistance for PrEP; if behaviorally eligible, provider will prescribe PrEP once eligibility is confirmed after reviewing lab results). The tester performs any specimen collection, weight measurements, etc. The tester and provider are in private settings during telemedicine appointments to ensure the privacy of the client.

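### Does blocking the allocation by site put arm balance at risk now that any King County PrEP provider may refer participants?

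*Protocol*

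**What the plan says.** Under Randomization in section 5.1, the allocation is "generated by site using blocked randomization with variable block sizes and random number generator". The draw is central: "The research coordinator will open a sequentially numbered, sealed envelope with the study allocation", after consent and after the baseline survey is complete. Sections 2.7 and 5.1 set a maximum of 20 participants per arm, so 40 in all.

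Section 3.1 first names two non-UW sites and then widens the field: "we propose to broaden study sites to any provider or organization in King County who provides PrEP". The reason given is that the two clinics had seen very few eligible people. The same section says "We will still operate the study out of Gay City and Kelley-Ross pharmacy", and that an added provider contacts the study team when someone is interested. Section 4.1 repeats the wider rule: "Participants will be recruited at sites in King County that offer PrEP, including Gay City and Kelley-Ross".

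Section 8.2 covers consent for people seen elsewhere, where UW staff are asked to step in: "If the staff has a time conflict or are at a site outside of Gay City or Kelley-Ross the clinic staff will reach out". Consent may then be taken where the person was seen, or elsewhere: "in another private location at UW or with a community partner (e.g., a private room at Gay City").

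No section says whether an added provider has its own list, shares a pooled list, or draws on one of the two clinics' lists.

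**The concern.** Blocking within site keeps arm sizes close only if blocks are mostly completed. Section 3.1 uses the term study sites for the added providers. Read literally with section 5.1, each one becomes a stratum with its own envelopes. A provider that sends one or two people never finishes a block, and the sum of many unfinished blocks behaves much like coin tossing. Section 8.2 adds a second uncertainty: the referring provider and the place of consent can differ, so either might be taken as the site.

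Two things would be at stake. Arm sizes could differ noticeably in a trial of 40, so that one arm passes its maximum of 20 or fills early. The coordinator would also find no rule in this protocol for choosing the envelope series for a referred participant. The low yield that prompted the widening makes small contributions per provider plausible.

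**Working it through.** **Inputs from the protocol.** Maximum 20 + 20 = 40 participants (sections 2.7 and 5.1); variable blocks by site, sizes not given (section 5.1); two named clinics plus an open-ended set of providers (section 3.1). No power, effect size or sample-size calculation is stated, so there is no figure of the plan's own to reproduce beyond 40.

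**Assumptions.** Equal allocation, implied by 20 and 20. Block sizes drawn at random from {2,4}, {4,6} or {2,4,6}; ranges below span the three sets. The numbers of lists and participants per list are also assumed.

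**Method.** Permuted blocks were simulated with an independent list per site, 20,000 runs per scenario. With d the difference in arm sizes, information relative to 20:20 is 4·n1·n2/40² = 1 − d²/1600.

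- 22:18 gives 4·22·18/1600 = 0.990
- 23:17 gives 4·23·17/1600 = 0.9775
- 24:16 gives 4·24·16/1600 = 0.960
- 26:14 gives 4·26·14/1600 = 0.910

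| Assumed participants per list (total 40) | Chance of 23:17 or worse | Mean information loss |
|---|---|---|
| One list | 0 | at most 0.1% |
| Two lists, 20/20 or 23/17 | 0 | 0.1% |
| Two clinics plus one pooled list, 15/13/12 | 0 to 0.3% | 0.2% |
| Same structure, 12/8/20 or 16/14/10 | 0 to 0.4% | not recorded |
| 12/8 plus five providers of 4 | 0.4% to 4.0% | not recorded |
| 16/14 plus five providers of 2 | 1.8% to 9.3% | not recorded |
| 15/13 plus six providers of 2 | 3.8% to 13.2% | 0.4% to 0.7% |
| 15/13 plus twelve providers of 1 | 18.2% to 19.0% | 0.9% |
| 11/9 plus twenty providers of 1 | 28.8% to 28.9% | 1.4% |
| Forty lists of 1 (simple randomisation, exact) | 43.0% | 2.5% |

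**Check on the last row.** Under simple randomisation the variance of d equals 40, so the expected loss is 40/1600 = 2.5%, the worth of one participant in 40. The simulation gave 2.4% to 2.6%. The exact chance of 23:17 or worse is 2·P(X ≤ 17), with X binomial (40, 0.5), which is 0.430.

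**How far exact balance was ever assured.** Two clinic lists alone do not guarantee 20:20, because the last block on each list may be unfinished. With 20/20 per list, exact balance occurred in 63% to 79% of runs; with 23/17 per list, in 48% to 50%.

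**Which reading fits the text.** The study continues to run from the two clinics. Outside providers contact the team, UW staff may take the consent of people seen outside the two clinics, and one coordinator opens the envelopes. A separate numbered series for each member of an open-ended set of providers would be awkward to prepare in advance. Two lists, or two plus a pooled list, fit this workflow with no extra machinery. Those are the rows where a 23:17 split is very rare or impossible.

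**The case for a change.** The strongest contrary argument is that this is more than a detail left for later. The protocol fixes a by-site rule, changes what counts as a site, and leaves the rule as it was. Choosing the envelope is an enrolment step, and section 5.1 is where that step is described. One sentence would settle it, and an accurate report of the randomisation needs to say which list was used.

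The observation stands: this protocol gives no mapping from provider to list. It does not follow that the trial has no such rule. The document is an ethics application asking for lay language, and it points to other study documents held separately. By-site blocking and a wider set of sites are compatible.

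The practical point about the maximum of 20 per arm is also fair, but those figures are upper limits, and two lists alone often miss an exact 20:20. Uncertainty about which series to open does not bias the allocation, since the envelopes are sealed and numbered and the block sizes vary.

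Replacing site lists with one central list would give up balance within clinic in mid-trial to recover a percent or two of information at most. Section 1.8 also notes "As the study enrollment date is ending", so few allocations may remain.

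**Conclusion.** No change to the plan follows. The gap is real but small: a missing list-to-provider mapping that the team running the envelopes can fill sensibly. Allocation remains random, concealed and unbiased under every reading.

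On the reading that best fits the workflow, two lists or two plus a pooled one, the chance of 23:17 or worse is between 0 and 0.4%. On the literal reading with many tiny providers it can reach about 29%, yet the mean information loss in the simulated provider mixes is 1.4% or less, and simple randomisation bounds it at 2.5% exactly (2.6% at most in simulation). A 26:14 split or worse, which would keep 91% of the information, occurred in at most 1.8% of runs in any provider mix for which it was recorded.

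These figures rest on assumed block sizes and provider counts and on a full 40 participants. The protocol supports none of the heavily fragmented mixes; section 3.1 gives three examples of added providers, one of them a category of private practitioners. For a pilot of acceptability and feasibility with no stated power target, losses of this size would not alter what the trial can conclude.
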